Appendix 1 Scheduled Clinical Laboratory Parameters

Biochemistry (Serum¹)		Hematology (Whole Blood ¹)		Urinalysis (Urine²)
Category	Parameters	Category	Parameters	Parameters
Hepatobiliary	Alanine aminotransferase	Red blood cells	Hematocrit	Blood
Hepatobiliary	Albumin	Red blood cells	Hemoglobin	Glucose
Hepatobiliary	Alkaline phosphatase	Red blood cells	Mean cell volume	Nitrites
Hepatobiliary	Aspartate aminotransferase	Red blood cells	Mean corpuscular hemoglobin	рН
Electrolytes and proteins	Calcium	Coagulation parameter	Platelets	Protein
Renal	Creatinine	Red blood cells	Red blood cell count	White blood cells
Hepatobiliary	Gamma-glutamyl transferase	White blood cells parameters	White blood cell count with automated differential	Specific gravity
Electrolytes and proteins	Potassium			Ketones
Electrolytes and proteins	Sodium			Urobilinogen
Hepatobiliary	Total bilirubin			Bilirubin
Electrolytes and proteins	Total protein			
Renal	Urea (blood urea nitrogen)			
Coagulation parameters	Prothrombin time (plasma4)			

¹Analyzed at a central laboratory.

²Analyzed at the trial site by use of a dipstick (if allowed per local regulations).

⁴Analyzed at Screening (Visit 1) only.

Appendix 2 Unscheduled Clinical Laboratory Parameters

Biochemistry (Serum)		Hematology (Whole Blood)		Urinalysis (Urine)
Category	Parameters	Category	Parameters	Parameters
Hepatobiliary	Alanine aminotransferase	Red blood cells	Hematocrit	Blood
Hepatobiliary	Albumin	Red blood cells	Hemoglobin	Glucose
Hepatobiliary	Alkaline phosphatase	Red blood cells	Mean cell volume	Nitrites
Hepatobiliary	Aspartate aminotransferase	Red blood cells	Mean corpuscular hemoglobin	рН
Electrolytes, proteins and creatinine kinase	Calcium	Coagulation parameter	Platelet count	Protein
Renal	Creatinine	Red blood cells	Red blood cell count	White blood cells
Hepatobiliary	Gamma-glutamyl transferase	White blood cells parameters	White blood cell count	Specific gravity
Electrolytes, proteins and creatinine kinase	Potassium	White blood cells parameters	Total neutrophil count	Ketones
Electrolytes, proteins and creatinine kinase	Sodium	White blood cells parameters	Monocyte count	Urobilinogen
Hepatobiliary	Total bilirubin	White blood cells parameters	Lymphocyte count	Bilirubin
Electrolytes, proteins and creatinine kinase	Total protein	White blood cells parameters	Basophil count	Squamous epithelial cells
Renal	Urea (blood urea nitrogen)	White blood cells parameters	Eosinophil count	Mucus
Coagulation parameters	Prothrombin time (plasma4)			Microscopy
Hepatobiliary	Amylase			Leucocyte esterase
Electrolytes, proteins and creatinine kinase	chloride			Color
Electrolytes, proteins and creatinine kinase	Bicarbonate			Appearance
Lipids	HDL-Cholesterol			Bacteria
Lipids	LDL-Cholesterol			

GWSP18023___V1.0_22 Mar 2022_Statistical Analysis Plan_ | VV-TMF-117088

Biochemistry	r (Serum)	Hematology (Whole Blo	ood)	Urinalysis (Urine)
Lipids	Total Cholesterol			
Lipids	Triglycerides			
Hepatobiliary	Lipase			
Electrolytes and proteins	Magnesium			
Electrolytes, proteins and creatinine kinase	Phosphorus			
Renal	Creatinine clearance			
Endocrinology	Insulin-like growth factor-1			
Endocrinology	Prolactin			
Renal	Estimate glomerular filtration rate			
Coagulation	INR			
Endocrinology	Glucose			
Electrolytes, proteins and creatinine kinase	Creatinine Kinase			
Immunology	HBaAg			
Immunology	HCV			
Immunology	HIV			

Appendix 3Toxicity Criteria for Laboratory Hematology andCoagulation Parameters based on CTCAE version 5.0

Laboratory Toxicity	Grade 1	Grade 2	Grade 3	Grade 4	
Hematology	Hematology				
Anemia	<lln 6.2="" l<="" mmol="" td="" –=""><6.2 – 4.9 mmol/L	<4.9 mmol/L		</lln>	<6.2 – 4.9 mmol/L	<4.9 mmol/L		
(Hemoglobin	<lln -="" 100="" g="" l<="" td=""><100 - 80 g/L	<80 g/L		</lln>	<100 - 80 g/L	<80 g/L		
Decreased)	<lln 10.0="" g="" l<="" td="" –=""><10.0 to 80.0 g/dL	<8.0 g/dL		</lln>	<10.0 to 80.0 g/dL	<8.0 g/dL		
Hemoglobin increased	Increase in >0 - 2 g/dL	Increase in >2 - 4 g/dL	Increase in >4 g/dL		
White Blood Cells	<lln 3000="" mm3<="" td="" –=""><3000 - 2000/mm3	<2000 - 1000/mm3	<1000/mm3	</lln>	<3000 - 2000/mm3	<2000 - 1000/mm3	<1000/mm3	
Decreased	<lln 109="" 3.0="" l<="" td="" x="" –=""><3.0 – 2.0 x 109/L	<2.0 – 1.0 x 109/L	<1.0 x 109/L	</lln>	<3.0 – 2.0 x 109/L	<2.0 – 1.0 x 109/L	<1.0 x 109/L	
Neutrophils count	<lln 1500="" mm3<="" td="" –=""><1500 - 1000/mm3	<1000 - 500/mm3	<500/mm3	</lln>	<1500 - 1000/mm3	<1000 - 500/mm3	<500/mm3	
Decreased	<lln 1.5="" 109="" l<="" td="" x="" –=""><1.5 – 1.0 x 109/L	<1.0 – 0.5 x 109/L	<0.5 x 109/L	</lln>	<1.5 – 1.0 x 109/L	<1.0 – 0.5 x 109/L	<0.5 x 109/L	
Lymphocytes count	<lln 800="" mm3<="" td="" –=""><800 – 500/mm3	<500 - 200/mm3	<200/mm3	</lln>	<800 – 500/mm3	<500 - 200/mm3	<200/mm3	
Decreased	<lln 0.8="" 109="" l<="" td="" x="" –=""><0.8 – 0.5 x 109/L	<0.5 – 0.2 x 109/L	< 0.2 x 109/L	</lln>	<0.8 – 0.5 x 109/L	<0.5 – 0.2 x 109/L	< 0.2 x 109/L	
Lymphocyte count increased		>4000/mm3-20,000/mm3 >4 - 20 x 109/L	>20,000/mm3 > 20 x 109/L		
Platelets count	<lln 75,000="" mm3<="" td="" –=""><75,000 – 50,000/mm3	<50,000 – 25,000/mm3	<25,000/mm3	</lln>	<75,000 – 50,000/mm3	<50,000 – 25,000/mm3	<25,000/mm3	
Decreased	<lln 109="" 75.0="" l<="" td="" x="" –=""><75.0 – 50.0 x 109/L	<50.0 – 25.0 x 109/L	<25.0 x 109/L	</lln>	<75.0 – 50.0 x 109/L	<50.0 – 25.0 x 109/L	<25.0 x 109/L	
Activated partial thromboplastin time prolonged (aPTT)	>ULN – 1.5 x ULN	>1.5 – 2.5 x ULN	>2.5 ULN		
Appendix 4Toxicity Criteria for Laboratory Biochemistry andUrinalysis Parameters based on CTCAE version 5.0

Laboratory Toxicity	Grade 1	Grade 2	Grade 3	Grade 4
Chemistry				
Sodium Increased (Hypernatremia)	>ULN - 150 mmol/L	>150 - 155 mmol/L	>155 - 160 mmol/L	>160 mmol/L
Sodium Decreased (Hyponatremia)	<lln -="" 130="" l<="" mmol="" td="">	<130 - 120 mmol/L	<120 mmol/L	</lln>		<130 - 120 mmol/L	<120 mmol/L
Potassium Increased (Hyperkaliemia)	>ULN - 5.5 mmol/L	>5.5 - 6.0 mmol/L	>6.0 - 7.0 mmol/L	>7.0 mmol/L;
Potassium Decreased (Hypokaliemia)	<lln -="" 3.0="" l<="" mmol="" td=""><lln -="" 3.0="" l<="" mmol="" td=""><3.0 - 2.5 mmol/L	<2.5 mmol/L	</lln>	</lln>	<lln -="" 3.0="" l<="" mmol="" td=""><3.0 - 2.5 mmol/L	<2.5 mmol/L	</lln>	<3.0 - 2.5 mmol/L	<2.5 mmol/L
Calcium Increased (Hypercalcemia)	>ULN - 11.5 mg/dL; >ULN - 2.9 mmol/L lonized calcium >ULN - 1.5 mmol/L	>11.5 - 12.5 mg/dL; >2.9 - 3.1 mmol/L lonized calcium >1.5 - 1.6 mmol/L	>12.5 - 13.5 mg/dL; >3.1 - 3.4 mmol/L; lonized calcium >1.6 - 1.8 mmol/L	>13.5 mg/dL; >3.4 mmol/L; Ionized calcium >1.8 mmol/L
Calcium Decreased (Hypocalcemia)	<lln -="" 8.0="" dl;
<lln -="" 2.0="" l;
lonized calcium <uln 1.0="" l<="" mmol="" td="" –=""><8.0 - 7.0 mg/dL; <2.0 - 1.75 mmol/L lonized calcium <1.0 - 0.9 mmol/L	<7.0 - 6.0 mg/dL; <1.75 - 1.5 mmol/L; lonized calcium <0.9-0.8 mmol/L	<6.0 mg/dL; <1.5 mmol/L; lonized calcium <0.8 mmol/L	</uln></lln></lln>	<8.0 - 7.0 mg/dL; <2.0 - 1.75 mmol/L lonized calcium <1.0 - 0.9 mmol/L	<7.0 - 6.0 mg/dL; <1.75 - 1.5 mmol/L; lonized calcium <0.9-0.8 mmol/L	<6.0 mg/dL; <1.5 mmol/L; lonized calcium <0.8 mmol/L
Albumin Decreased (hypoalbuminemia)	<lln -="" 3="" dl;
<lln -="" 30="" g="" l<="" td=""><3 - 2 g/dL; <30 - 20 g/L	<2 g/dL; <20 g/L		</lln></lln>	<3 - 2 g/dL; <30 - 20 g/L	<2 g/dL; <20 g/L	
Alkaline Phosphatase increased	>ULN - 2.5 x ULN if baseline normal 2.0 - 2.50 x baseline if baseline abnormal	>2.5 - 5.0 x ULN if baseline normal >2.5 - 5.0 x baseline if baseline abnormal	>5.0 - 20.0 x ULN if baseline normal >5.0 – 20.0 x baseline if baseline abnormal	>20.0 x ULN if baseline normal 20.0 x baseline if baseline abnormal
Alanine amino transferase increased	>ULN - 3.0 x ULN if baseline normal 1.5 - 3.0 x baseline if baseline abnormal	> 3.0 - 5.0 ULN if baseline normal >3.0 - 5.0 x baseline if baseline abnormal	>5.0 – 20.0 x ULN if baseline normal >5.0 - 20.0 x baseline if baseline abnormal	>20.0 x ULN if baseline normal > 20.0 x baseline if baseline abnormal
Aspartate amino transferase increased	>ULN - 3.0 x ULN if baseline normal 1.5 - 3.0 x baseline if baseline abnormal	 > 3.0 - 5.0 ULN if baseline normal >3.0 - 5.0 x baseline if baseline abnormal 	>5.0 – 20.0 x ULN if baseline normal >5.0 - 20.0 x baseline if baseline abnormal	>20.0 x ULN if baseline normal > 20.0 x baseline if baseline abnormal
Blood Bilirubin Increased	>ULN – 1.5 x ULN if baseline normal >1.0-1.50 x baseline if baseline abnormal	>1.5 – 3.0 x ULN if baseline normal >1.5-3.0 x baseline if baseline abnormal	>3.0 – 10.0 x ULN if baseline normal >3.0- 10.0 x baseline if baseline abnormal	>10.0 x ULN if baseline normal > 10.0 x baseline if baseline abnormal
Gamma Glutamyl Transferase Increased	>ULN - 2.5 x ULN if baseline normal	>2.5 - 5.0 x ULN if baseline normal	>5.0 - 20.0 x ULN if baseline normal	>20.0 x ULN if baseline normal

Statistical Analysis Plan for Protocol GWSP18023 (22-MAR-2022)

Laboratory Toxicity	Grade 1	Grade 2	Grade 3	Grade 4
	2.0 - 2.5 x baseline if baseline abnormal	>2.5 - 5.0 x baseline if baseline abnormal	>5.0 - 20.0 x baseline if baseline abnormal	>20.0 x ULN if baseline abnormal
Creatinine Increased	>ULN – 1.5 x ULN	>1.5 - 3.0 x baseline; >1.5 – 3.0 x ULN	>3.0 baseline; >3.0 – 6.0 x ULN	>6.0 x ULN
Chronic Kidney Disease	eGFR (estimated Glomerular Filtration Rate) or CrCl (creatinine clearance) <lln -="" 60
ml/min/1.73 m2 or proteinuria 2+ present; urine protein/creatinine >0.5</lln>	eGFR or CrCl 59 - 30 ml/min/1.73 m2	eGFR or CrCl 29 - 15 ml/min/1.73 m2	eGFR or CrCl <15 ml/min/1.73 m2
Hypoalbuminemia	<lln -="" 3="" dl;
<lln -="" 30="" g="" l<="" td=""><3 - 2 g/dL; <30 - 20 g/L	<2 g/dL; <20 g/L		</lln></lln>	<3 - 2 g/dL; <30 - 20 g/L	<2 g/dL; <20 g/L	
Proteinuria	1+ proteinuria	2+ and 3+ proteinuria	4+ proteinuria	

Appendix 5Prohibited Medications Solely Metabolized byUGT1A9 and UGT2B7 and Determination Criteria

Examples of medications that are solely metabolized by UGT1A9 and UGT2B7 and prohibited for the duration of the trial are provided in below.

Medications solely metabolized by UGT1A9		Medications sol	lely metabolize	d by UGT2B7
Medication name	ATC code	Medication name	ATC code	Comments
Flavopiridol		Benoxaprofen	M01AE06	
Propofol	N01AX10	Carbamazepine	N03AF01	
		Codeine	R05DA12	
			R05DA04	
			NI02A I01	
			N02AJ02	
			N02AJ02	
			N02A.107	
			N02AJ08	
			N02AJ09	
			N02AA08	
			N02AA58	
			N02AA59	
			N02AA79	
		Cyclosporin A	L04AD01,	
			S01XA18	
		Epirubicin	L01DB03	
		Indomethacin	C01EB03	
			M01AB01	
			M01AB51	
			M02AA23	
			S01BC01	
			S01CC02	S01CC02 also contains anti-infective medications
		Tacrolimus	D11AH01	
			L04AD02	
		Tiaprofenic acid	M01AE11	
		Zaltoprofen	M01A	With verbatim (reported) term containing "ZALTOPROFEN"
		Zomepirac	M01AB04	
		Zidovudine	J05AF01	
			J05AR01	Combination product
			J05AR04	Combination product
			J05AR05	Combination product

ATC = Anatomic Therapeutic Class

Appendix 6 Prohibited Medications Strong CYP3A4 Inducers and Determination Criteria

Strong CYP3A4 inducers		
Medication name	ATC code	Comments
Rifampicin	J04AB02 J04AB03 J04AM02 J04AM05 J04AM06 J04AM07 A07AA13* D06AX15* S01AA16* S02AA12*	This is a list on rifampicin only but also on products which contain rifampicin * refers to rifamycin
carbamazepine	N03AF01	
phenytoin	N03AB02 N03AB04 N03AB05 N03AB52	
phenobarbital,	N03AA01 N03AA02	
St John's Wort (hypericum perforatum)	N06AX25	

ATC = Anatomic Therapeutic Class

Appendix 7 Other Prohibited Medications and Determination criteria

Other prohibited medication			
Medication name	ATC code	Verbatim code	Comments
Nabiximols, cannabis or cannabinoid-based derived product	N03AX24		N03AX24: group of other anti- epileptics and cannabidiol is one of them
	N02BG10		This is the greater group of analgesics, and N02BG10 is a cannabinoid
Botulinum toxin injections,	M03AX01	Contains: 'BO' and 'Tox' '"Dysport 'Xeomin	Muscle relaxant products
Antipsychotic medications,	N05A apart from N05AN (Lithium) Including N05AH02 (BDZ)		
Benzodiazepines (if not following protocol requirements)	N03AE N05BA N05CD M03BX07		N03AE: clonazepam N05BA: broader group of anxiolytics contain the main used BDZ N05CD broader group of hypnotics but also contains melatonin for instance. M03BX07: tetrazepam

BDZ=Benzodiazepines

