# 8.2.1 Concomitant Optimized Multiple Sclerosis Antispasticity Medications

As nabiximols is being investigated as therapy in patients with spasticity due to MS, all patients must currently be taking at least 1 optimized oral antispasticity medication. Optimized oral antispasticity medications will include at least baclofen, tizanidine, or dantrolene (monotherapy or combination therapy). Their antispasticity medication must have been stable for at least 30 days prior to Screening (Visit 1) and the medication is expected to remain stable through the duration of the trial. However, despite this optimization, eligible patients do not have adequate relief of their spasticity symptoms, including muscle spasms. Optimization of antispasticity medications is defined as having reached the most efficacious and best tolerated dose according to the relevant local prescribing information. The patient must be willing to maintain the same antispasticity therapy for the duration of the trial.

Benzodiazepine use is allowed if doses and dosing regimen have been stable for at least 30 days prior to Visit 1.

If the patient is currently receiving an MS disease-modifying therapy or dalfampridine or fampridine, it must be at a stable dose for at least 3 months prior to Visit 1 and is expected to remain stable for the duration of the trial.

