# 8.3 Prohibited Therapy During Trial Period

The following medications are prohibited for the duration of the trial:

- Cannabis use for medical or recreational purposes or any cannabinoid-based medication within 30 days of Visit 1 and for the duration of the trial
- Botulinum toxin injection for the relief of spasticity within 6 months of Visit 1 and for the duration of the trial
- Antipsychotic medication
- Any benzodiazepines use on an as-needed (PRN) basis

- Drugs that are solely metabolized by UGT1A9 and UGT2B7 (See APPENDIX 4)
- Strong CYP3A4 inhibitors or inducers (e.g., rifampicin, carbamazepine, phenytoin, phenobarbital, St John's Wort)

Any patient taking these medications after Visit 1 must cease IMP and should remain in the trial.

The use of psychotropic medications other than those specified above would be allowed provided the medication is used on a daily basis, has been at a stable dose for at least 30 days or 5 half-lives (whichever is longer) prior to Visit 1 and is expected to remain stable throughout the trial.

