12.3.2 Prior, Concomitant and Prohibited Medications

For any medications/nondrug therapies initiated or ongoing since Visit 1 (Screening), the start and stop date, dose, unit, frequency, route of administration, and indication will be recorded respectively in the 'Concomitant Medication' eCRF page and in the 'Concomitant Physiotherapy' eCRF page.

As nabiximols is being investigated as therapy in patients with spasticity due to MS, all patients must currently be taking at least 1 optimized oral MS antispasticity medication. Optimized oral MS antispasticity medications will include at least baclofen, tizanidine, and/or dantrolene (monotherapy or combination therapy). Their MS antispasticity medication must have been stable for at least 30 days prior to Screening (Visit 1) and the medication is expected to remain stable throughout the duration of the trial.

All Medications will be categorized by medication anatomic and therapeutic class (ATC) according to the most current version of World Health Organization-Drug Dictionary (WHO-DD) global March 2020 Dictionary Version B3 or higher according to the version in use at the time of database lock.

Medication used for MS will also be categorized according to information recorded in the CRF as:

- Disease modifying drug,
- Anti-spasticity drug (baclofen, tizanidine, dantrolene, benzodiazepine, muscle relaxants, botulinum toxin, gabapentin, pregabalin),
- Other MS symptoms.

Whereas physiotherapy used will be categorized according to the reason recorded in CRF as:

- Spasticity,
- Adverse events (other than spasticity),
- Other MS symptoms,
- Other symptoms not associated MS.

Patients should stop taking any prohibited therapy prior to Screening (Visit 1) and also within 30 days of Visit 1 for cannabis for medical or recreational purposes or any cannabinoid-based medication. These medications are prohibited for the duration of the trial.

Prohibited medications are categorized as:

- Nabiximols, cannabis or cannabinoid-based derived product (see Appendix 7),
- Botulinum toxin injections (see Appendix 7),
- Antipsychotic medications (see Appendix 7),
- Benzodiazepines (if not following protocol requirements) (see Appendix 7),
- Medications that are solely metabolized by UGT1A9 (see Appendix 5),
- Medications that are solely metabolized by UGT2B7 (see Appendix 5),
- Strong CYP3A4 inducers or inhibitors (eg, rifampicine, carbamazepine, phenytoin, phenobarbital, St John's Wort) (see Appendix 6).

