In order to flag prohibited medications taken in the study, each medication taken will be compared against a pre-specified list of all prohibited medications as presented in Appendix 5, Appendix 6 and Appendix 7 along with their determination criteria.

All medications/ non-drug therapy (eg, physiotherapy) will be classified as follows:

- Prior medications are those the patient used prior to the IMP Start Date and discontinued before first administration.
- Current medications are those that the patient used at time of randomization and at the same time as IMP intake. This classification will mainly be used to summarize MS medications.
- Concomitant medications are any medications / non-drug therapies that are ongoing at the time
 of first dose; these medications can be initiated
 - Before first intake of study medication.
 - At the same time of study medication.
- Post treatment medications (FU medications) are any medications /non-drug therapies initiated following IMP End Date.

In order to classify each therapy in case of missing / partial start and /or stop date, imputation rules as described in Section 10.15 will be applied.

All medications / non-drug therapies (including physiotherapies) taken during the trial will be summarized by treatment arm for the SAF. If it appears that the randomized treatment arm is different from the actual treatment arm and/or if patients belonging to the SAF are different from those belonging to the FAS. All the summaries will be presented using both study populations.

The number and percentage of patients using each medication along with the number and percentage of patients using at least one medication within each medication group will be summarized.

All medications and all physiotherapy will be separately listed.

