13	Exclusion criteria	Did not respond adequately to treatment with nabiximols or another cannabis-based medication if exposed at any time before the 30-day period prior to Visit 1.
14*	Exclusion criteria*	Has any other clinically significant disease or disorder (including seizure disorder) that, in the opinion of the investigator, may put the patient, other patients, or site staff at risk because of participation in the trial, influence the interpretation of trial results, or may affect the patient's ability to take part in the trial.
		For certain disorders, determined with medical monitor
15	Study drug	Patient failing to acknowledge in the mobile health platform (MHP) that they have taken at least one spray on 4 or more days out of any 7 consecutive days within days 57 to 84.
16	Study drug	Patient randomized but not exposed to study drug
17	Study drug	Patients exposed outside of randomization call to IRT.
18	Study drug	Patient receiving a kit number which is not the treatment he/she was allocated to by IRT.
19	Efficacy endpoint data	Missing evaluable average daily spasm count pre-dose assessment
20	Efficacy endpoint data	Missing evaluable post baseline average daily spasm count assessment
21	Efficacy endpoint data	Missing evaluable on-treatment Day 85 (between Day 57 and Day 85) average daily spasm count assessment
22	Prohibited medication	Patient taking antipsychotic medication at any time during the trial.
23	Prohibited medication	Patient taking benzodiazepine on an as needed (PRN) basis during the trial
24	Prohibited medication	Patient taking commercial cannabis or any cannabinoid medication during the trial.
25	Prohibited medication	Patient taking botulinum injection during the trial
26	Prohibited medication	Initiation or changes in the dose of MS disease modifying therapy any time after randomization at Visit 2
27	Prohibited medication	Initiation of a new course of physiotherapy any time after Visit 1
28	Prohibited medication	Patient taking drugs solely metabolized by UGT1A9 and UGT2B7 during the trial
29	Prohibited medication	Patient taking strong CYP3A4 inducer or inhibitor during the trial
30	Prohibited medication	Patient changing dose or introducing antispasticity medication (baclofen, tizanidine, dantrolene)
31	Prohibited medication	Patient changing dose or introducing dalfampridine or fampridine
32	Randomization irregularities	Deviation description with regards to randomization specification

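### The SAP drops the protocol's spasticity limit on botulinum toxin, so an injection the protocol does not prohibit would be reported as prohibited

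*SAP*

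**What the plan says.** Protocol 8.3 prohibits "Botulinum toxin injection for the relief of spasticity within 6 months of Visit 1 and for the duration of the trial". Exclusions 7 and 8 in Protocol 6.2 carry the same restriction to spasticity.

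SAP 12.3.2 sets the flagging method: "each medication taken will be compared against a pre-specified list of all prohibited medications as presented in Appendix 5, Appendix 6 and Appendix 7", together with the determination criteria given there. Its list of prohibited categories names botulinum toxin without a condition. The Appendix 7 row, "Botulinum toxin injections", gives ATC code M03AX01 and a verbatim search on fragments of the drug name and two brand names. In SAP 12.4, Table 12.4-2 item 25 reads "Patient taking botulinum injection during the trial", and major deviations decide who leaves the per-protocol set.

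SAP 12.3.2 also says that for each medication "the start and stop date, dose, unit, frequency, route of administration, and indication will be recorded". SAP 6.2 reports no change from the protocol.

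**The concern.** The prohibited-medication tables are meant to show how far patients departed from the protocol. If the SAP's rule is wider than the protocol's, those tables count as violations some things that were not violations.

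The consequence is not only cosmetic. Protocol 8.3 requires a patient who takes a prohibited drug after Visit 1 to stop IMP and remain in the trial. A patient wrongly flagged who stayed on IMP would look like a site that failed to apply that rule. By the wording of item 25, the same patient would also be listed with a major deviation and removed from the per-protocol set.

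**Working it through.** No formula or planned figure is involved, so the check compares texts.

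| Place | Limited to spasticity? |
|---|---|
| Protocol 6.2, exclusions 7 and 8 | Yes |
| Protocol 8.3 | Yes |
| SAP 12.3.2, category list | No |
| SAP Appendix 7, botulinum row | No: ATC code or name only |
| SAP Table 12.4-2, item 25 | No |
| SAP 6.2, changes from protocol | None declared |

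**Test record A:** botulinum toxin after Visit 1, recorded indication spasticity. Protocol 8.3 prohibits it and Appendix 7 flags it. The documents agree.

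**Test record B:** the same drug and timing, recorded indication something else.
1. Protocol 8.3 does not prohibit it.
2. Appendix 7 matches it on M03AX01 or the product name, and nothing in the row releases it.
3. It is counted in the SAP 12.3.2.3 prohibited-medication tables.
4. Under item 25 as worded it is a major deviation, and SAP 12.4 then removes the patient from the per-protocol set.

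The documents disagree only on record B. Protocol 3.1 lists several common MS symptoms besides spasticity, bladder dysfunction and pain among them. Treatment for another reason is therefore foreseeable, although the documents never mention botulinum toxin for those symptoms.

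**What survives early termination.** Addendum Table 7-1:
- keeps SAP 12.3.2, apart from post-treatment medication summaries;
- keeps SAP 12.4, apart from summaries of major deviations, so the deviation listing that identifies them remains;
- keeps SAP 12.1, which counts and lists analysis-set membership;
- drops sensitivity and supplemental analyses, which include the per-protocol MMRM.

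**Size.** No usage count is given. With 223 patients per arm, one mislabelled patient adds 100/223 = 0.45 percentage points to that arm's prohibited-use figure. If 0% to 3% of patients had a non-spasticity injection (an assumption), that is 0 to 223 × 0.03 = 6.7 patients per arm. Recruitment stopped before the planned number, so the counts would be lower and the weight of each patient higher.

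**Secondary check, benzodiazepines.** Protocol 8.3 prohibits "Any benzodiazepines use on an as-needed (PRN) basis", while Protocol 8.2.1 states "Benzodiazepine use is allowed if doses and dosing regimen have been stable for at least 30 days prior to Visit 1". Appendix 7 labels its row "Benzodiazepines (if not following protocol requirements", so the condition is present. Beside it stand only four ATC codes (N03AE, N05BA, N05CD, M03BX07), with no rule for as-needed frequency or 30-day stability. The SAP's own comment says N05CD also covers melatonin, and nothing filters that out.

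**The case against.** **On item 25.** SAP 12.4 says important deviations are defined in a separate deviation guidance and drawn from an internal deviation system that the study team and sponsor review before lock. They are not generated by matching codes to Appendix 7. The guidance is not among the documents and may carry the spasticity limit. This stands as far as it goes: item 25 is wrong as worded, but its application cannot be judged. It does not help the SAP 12.3.2.3 tables, which do run on the Appendix 7 match.

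**On permitted use.** The protocol nowhere expressly permits botulinum toxin for other reasons, and exclusion 28 separately bars planned interventions or medication changes that may affect spasticity or MS. This also stands. The accurate statement is that Protocol 8.3 does not prohibit such use, not that the protocol endorses it.

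**Stronger readings a reader might infer.**
- That benzodiazepines are flagged by code alone, so that every patient on a stable regimen is reported as a violator. The documents do not support this. The Appendix 7 label and the SAP 12.3.2 category both carry the protocol condition, and Table 12.4-2 item 23 is limited to as-needed use. Only the working rule is missing.
- That the cannabis row would miss recreational use because it has two ATC codes and no verbatim search. That depends on how the drug dictionary codes such records, which the documents do not show. Item 24 also captures cannabis use separately.

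**Conclusion.** The botulinum point holds. SAP 12.3.2, Appendix 7 and item 25 are wider than Protocol 6.2 and 8.3, and SAP 6.2 does not declare the difference.

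The impact is limited to the retained prohibited-medication tables, the deviation listings and per-protocol set membership. A reader might infer that an efficacy result is at risk. None is: the primary MMRM runs on the full analysis set with all observed values, and the per-protocol repeat was already conditional on more than 10% exclusions before the addendum dropped it.

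The number affected is unknown and probably small. The conclusion assumes that Appendix 7 is programmed as written and that at least one injection is recorded with a reason other than spasticity. The benzodiazepine row is a request for detail, not a contradiction.

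**What to change.** Make the following changes before unblinding:

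1. **Appendix 7:** add to the botulinum row that the record is flagged only when the recorded indication is spasticity. Use the indication field, not the medication group, because SAP 12.3.2 names botulinum toxin under antispasticity drugs. Send records with a missing or unclear indication to blinded review.
2. **SAP 12.3.2 and Table 12.4-2 item 25:** word both to match Protocol 8.3, and confirm that the deviation guidance says the same.
3. **If the wider rule is intended:** reconcile it with the protocol and declare it in SAP 6.2. This review takes no position on which rule is clinically right.
4. **Secondary:** state how the benzodiazepine condition is applied from the collected fields, for example as-needed frequency, or a start or dose change later than 30 days before Visit 1. Remove melatonin from the N05CD match.

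The main change costs about three lines of text and one programming condition. The secondary change costs a few more. Indication, frequency, dose and dates are already collected, so no new data are needed.
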